12.0 Descriptive Factors

- Breast: left vs. right
- Tumor Size: 0-2cm vs 2-5cm
- Pathologic Lymph Nodes: N0 vs N1
- Pathologic complete response: yes vs. none ³¹

13.0 Treatment/Follow-up Decision at Evaluation of Patient

Follow-up data will be collected and entered after the observation phase outlined in section 4.0. If the patient is still alive after 5 years have elapsed from the on-study date, no further follow-up is required by this protocol.

- 13.1 Patients who have a recurrence while receiving therapy or during observation will go to the event-monitoring phase and be followed
- 13.2 Patients who discontinue treatment or observation for reasons other than recurrence will go to the event-monitoring phase and be followed
- 13.3 Patients who will not receive any radiation treatment or who will receive radiation treatment elsewhere will move to event monitoring phase.
- 13.4 A patient is deemed *ineligible* if after registration, it is determined that at the time of registration, the patient did not satisfy each and every eligibility criteria for study entry. The patient may continue treatment off-protocol at the discretion of the physician as long as there are no safety concerns, and the patient was properly registered. The patient will go directly to the event-monitoring phase of the study (or off study, if applicable).

If the patient received treatment, all data up until the point of confirmation of ineligibility must be submitted. Event monitoring will be required per Section 18.0 of the protocol.

If the patient never received treatment, on-study material and the End of Active Treatment/Cancel Notification Form must be submitted. No further data submission is necessary.

- 13.5 A patient is deemed a *cancel* if he/she is removed from the study for any reason before any study treatment is given. On-study material and the End of Active Treatment/Cancel Notification Form must be submitted. No further data submission is necessary.

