6.0 Registration

6.1 Registration Procedures

- 6.1.1 Patient will be registered to the study when they have consented, met eligibility criteria, and have been logged into the Research Participant Tracking (Ptrax) system.
- 6.1.2 Baseline tests/procedures (see section 4.0) will be completed within the guidelines specified on the test schedule.
- 6.1.3 All patients meeting eligibility criteria who have signed a consent form and who have completed treatment will be evaluable for the primary analysis. All patients completing treatment as per the study pre-op RT followed by breast conserving surgery will be used to determine the protocol accrual.
- 6.1.4 Patients consented and enrolled will be monitored in the registry, if patients signed our registry consent (IRB 16000492). All patient meeting accrual as defined in 6.1.3 will be analyzed per study.

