16.52 Secondary Analyses

16.521 *Acute adverse events (up to 180 days post-RT):* All patients who were registered to the study and started treatment will be included in the acute adverse event analysis. An acute adverse event is an AE, regardless of attribution, that occurs up to 180 days post-RT. The maximum grade for each type of acute AE will be recorded for each patient. Data will be summarized as frequencies and relative frequencies. Additionally, the relationship of the adverse event(s) to the study treatment will be taken into consideration.

16.522 *Late adverse events:* All patients who were registered to the study and started treatment will be included in the late adverse event analysis. A late adverse event is an AE, regardless of attribution, that after one month post-RT and up to 5 years post-RT. The maximum grade for each type of late AE will be recorded for each patient. Data will be

summarized as frequencies and relative frequencies by treatment arm. Additionally, the relationship of the adverse event(s) to the study treatment will be taken into consideration.

- 16.523 *Locoregional control:* The cumulative incidence of locoregional recurrence will be estimated using a competing risks method (Gooley et al.). The competing risks will be distant breast cancer recurrence and death.
- 16.524 *Invasive disease-free survival:* i-DFS is defined as the time from registration until the time of disease recurrence or death due to any cause. The i-DFS will be estimated with a Kaplan-Meier estimator and curve. Estimates will be given for specific time points along with 95% CIs.
- 16.525 *Disease-free survival:* DFS is defined as the time from registration until the time of disease recurrence or death due to any cause. The DFS will be estimated with a Kaplan-Meier estimator and curve. Estimates will be given for specific time points along with 95% CIs.
- 16.526 *Cause specific survival:* The CSS will be estimated with a Kaplan-Meier estimator and curve. Estimates will be given for specific time points along with 95% CIs.
- 16.527 *Overall survival:* The OS will be estimated with a Kaplan-Meier estimator and curve. Estimates will be given for specific time points along with 95% CIs.

16.53 Exploratory Analyses:

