18.0 Records and Data Collection Procedures

18.1 Submission Timetable

Initial Material(s)

CRF	Treatment (Compliance with Test Schedule Section 4.0)
Institutional Contacts	
Patient Eligibility	
Demographics	
On-Study	≤2 weeks after registration
Pathology of Ipsilateral Breast	
Adverse Events- Baseline	
Patient Status: Baseline	
Patient Assessment	
	*6 months after accrual
Off Treatment	Submit ≤2 weeks after registration if withdrawal/refusal occurs prior to beginning protocol therapy

Test Schedule Material(s)

CRF	End of Treatment	12 weeks post-RT / Observation Phase ⁴	Event Monitoring ⁵
Radiation Therapy	X		
Radiation Lumpectomy Therapy	X		
Patient Assessment	X	X	
Adverse Events Solicited	X	X	
Adverse Events: Other	X ²	X ²	
Off Treatment	X ²	X ²	
Patient Status Form	X	X	X
Specimen Submission: Tissue (Recurrence)		X ²	
Consent Withdrawal	X ²	X ²	
Lost to Follow-up	X ²	X ²	
Breast Radiotherapy Questionnaire ³	X	X	

- ¹ Complete at each evaluation during Active Treatment (see Section 4.0).
- ² When applicable
- ³ Survey will need to be entered manually if has not alternately been scanned or entered electronically
- ⁴ Active monitoring observation phase, Day 15 (+/- 3 days), D90 (+/- 1 month), D180 (+/- 2 months), D365 (+/- three months), annually for 4 years (+/- 6 months, total 5 years follow-up). If patient progresses within observation, they will move to the event monitoring phase where they will be followed until 5 years of follow-up information has been completed from the end of treatment time point.
- ⁵ If patient has a recurrence prior to being off radiation therapy for 5 years, continue to follow yearly.

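### Irradiated patients who stop early or are later found ineligible move to event monitoring, where section 18.1 marks no AE form, yet they stay in the AE analyses and the suspension rule

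*Combined protocol and SAP*

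**What the plan says.** **Routing.** Section 13.2: "Patients who discontinue treatment or observation for reasons other than recurrence will go to the event-monitoring phase and be followed". Stopping because of toxicity is not excepted. Section 13.4, on patients found after registration not to have met the criteria: "The patient will go directly to the event-monitoring phase of the study (or off study, if applicable"). If such a patient was treated, "all data up until the point of confirmation of ineligibility must be submitted", and event monitoring then follows section 18.0.

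**Forms.** In the section 18.1 table, "Adverse Events Solicited" and "Adverse Events: Other" are marked under End of Treatment and under the 12-week/observation column (the second one only when applicable). Under Event Monitoring the only marked row is "Patient Status Form X X X". Footnote 4 places the day 15, 90, 180, 365 and annual visits in the observation phase.

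**Analysis.** Section 16.521: "All patients who were registered to the study and started treatment will be included in the acute adverse event analysis", with a window to 180 days post-RT. Section 16.522 uses the same population for late AEs up to 5 years. Section 16.62 suspends accrual if 4 or more of the first 10 treated patients, or 6 at any point, have a listed treatment-related grade 3 or higher event or a poor cosmetic outcome. It looks at end of/during RT, 3 months, 12 months and yearly.

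**The concern.** The set of patients analysed is wider than the set for whom AE data are scheduled. A patient who received some radiation and then left the treatment pathway stays in the denominator, but after the move the visible text requires no AE form. Later dermatitis worsening, pneumonitis or an in-field wound infection in that patient could go unrecorded and be tabulated as no event.

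The AE proportions would then be biased downwards, and the suspension rule could reach its limits of 4 and 6 later than it should, or not at all. With limits that small, one or two unrecorded events can matter.

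**Working it through.** **1. Set the sections side by side, for a patient who has received at least one fraction.**

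| Question | Stops early (13.2) | Found ineligible (13.4) |
|---|---|---|
| Phase after the change | Event monitoring | Event monitoring, or off study |
| AE data up to the change | End of Treatment AE forms | All data to confirmation of ineligibility |
| AE forms after the change (18.1) | None marked | None marked |
| In the AE analyses (16.521, 16.522) | Yes | Yes |
| Counted by 16.62 | Yes, as a treated patient | Yes, as a treated patient |

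The mismatch is confined to the third row: events after the change of phase.

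**2. How many patients.** The plan gives no discontinuation rate. Section 16.42 allows 3 extra patients for ineligibility, cancellation, major treatment violation or other reasons: 3/25 = 12%. Cancellations are by definition (13.5) never treated and so lie outside the AE analyses. The range is therefore 0 to about 3.

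**3. Effect on an AE proportion.** Let the other 22 patients have rate p and the 3 have rate q, with nothing recorded for the 3.

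- True proportion = (22p + 3q)/25; reported = 22p/25; shortfall = 3q/25, at most 3/25 = 12 percentage points.
- p = q = 20%: true 5.0/25 = 20.0%, reported 4.4/25 = 17.6%.
- p = 20%, q = 100%: true 7.4/25 = 29.6%, reported 17.6%.

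**4. Effect on the suspension rule.** The plan states no operating characteristics for this rule, so there is no figure to reproduce. (The power table in 16.44 for the pCR rule does reproduce, but it is not at issue here.) The plan also gives no grade 3+ rate, so I assume 10%, 20% and 30%.

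With X1 the recorded events among the first 10 patients and X2 those among the next 15, both binomial:

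P(suspend) = P(X1 ≥ 4) + Σ (i = 0 to 3) P(X1 = i) × P(X2 ≥ 6 − i)

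Full capture uses n1 = 10 and n2 = 15. Losing 3 patients, one of them among the first 10, uses n1 = 9 and n2 = 13.

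| True rate | Full capture | 3 patients with no AE data |
|---|---|---|
| 10% | 0.013 + 0.027 = 0.040 | 0.008 + 0.015 = 0.023 |
| 20% | 0.121 + 0.278 = 0.399 | 0.086 + 0.198 = 0.284 |
| 30% | 0.350 + 0.464 = 0.814 | 0.270 + 0.428 = 0.698 |

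At 20%, losing one patient (in the first 10) gives 0.356 and losing two gives 0.319.

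The losses in steps 3 and 4 are upper bounds for up to 3 patients: they assume no AE data at all, whereas events up to the change of phase are collected (step 1).

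**The case against.** The strongest reply is that the controlling schedule cannot be seen. Section 10.4 ties AE grading to each evaluation and 11.1 ties evaluations to section 4.0, of which only footnotes survive in the available text. An empty cell in the 18.1 table is weaker evidence than a sentence would be. That stands as a caveat. Even so, if the 4.0 grid does schedule AE assessment in event monitoring, 18.1 disagrees with it.

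There are also safeguards. Section 10.3 requires a worksheet whenever an AE is identified, whatever the phase. Section 10.52 covers grade 4–5 events not listed in 10.4, and 10.53 covers deaths. Section 16.6 keeps the DSMB involved until all patients have 180 days of follow-up and promises 5-year follow-up. These narrow the gap, but none schedules a look for grade 1–3 events in a patient who has moved, and the suspension rule starts at grade 3.

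Three stronger readings are tempting and are not supported:

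- *The plan misses the very patients most likely to have toxicity.* The event that makes a patient stop belongs on the End of Treatment forms. No figure in the documents shows a higher later rate in early stoppers. Assuming a 50% rate in the 3 and 20% in the rest gives 0.572 with full capture against 0.284, but that again presumes nothing was recorded for them.
- *Removal from AE collection depends on the outcome in both groups.* Ineligibility under 13.4 is a fact about the time of registration. For that group this is incomplete capture, with no documented link to toxicity.
- *Follow-up depends on a separate consent.* Section 6.1.4 reads "Patients consented and enrolled will be monitored in the registry, if patients signed our registry consent". It concerns a registry with its own IRB number and does not make study follow-up conditional.

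**Conclusion.** The point holds in a narrow form, as a cheap improvement. On the visible text, irradiated patients moved early to event monitoring stay in the AE analyses and under the suspension rule with no AE form due after the move. The exposure is later events, mainly up to grade 3. For early stoppers the loss may be related to toxicity, although no figure in the documents shows it.

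The effect runs from nil, if no irradiated patient moves early, to at most 12 percentage points on an AE proportion. For the suspension rule, the probability of triggering drops by at most 0.017, 0.115 and 0.116 at assumed rates of 10%, 20% and 30% (0.040 − 0.023, 0.399 − 0.284, 0.814 − 0.698). These bounds rest on 3 affected patients, one of them in the first 10, no recorded AE data from any of them, and the same event rate in all 25. The conclusion also depends on the unseen section 4.0 grid not scheduling AE assessment during event monitoring.

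**What to change.** In 13.2 and 13.4, state that any patient who received at least one study fraction has both AE forms completed at the planned post-RT time points, whatever the reason for leaving treatment, unless consent is withdrawn. This should run at least through day 180, and also cover the later time points that 16.522 and 16.62 use. Say explicitly that these patients count in 16.62. Mark both AE rows accordingly in the Event Monitoring column of 18.1, and check that column against the section 4.0 grid. Beside the AE tables, report the number of patients with incomplete AE follow-up.

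Leave the registry consent in 6.1.4 as it is.

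The cost is a few sentences, two table marks, and AE follow-up for perhaps 0 to 3 patients who are off protocol treatment.

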14.0 Body Fluid Bio-specimens

14.1 Summary Table of Research Blood and Body Fluid Specimens to be Collected for this Protocol

Collection Tube	Volume to Collect per Tube (Total Number of Tubes to Collect)	Time point: Before radiation	Time point: After radiation
EDTA tubes	10 mL (8)	X(4)	X(4)
No additive tubes (for Serum)	10 mL (4)	X(2)	X(2)

14.2 BAP will process and store specimens per standard operating procedures. The baseline sample will be obtained prior to the start of radiation. It would be used as our control for the DNA exome sequencing section 17.0.

14.3 We will send to Rochester two EDTA tubes with 10cc of blood taken prior to radiation and two after radiation for a total of 4 EDTA tubes.

15.0 Drug Information

Not Applicable

16.0 Statistical Considerations and Methodology

16.1 Overview: This is a phase II trial to determine the pathologic complete response (pCR) rate (at time of definitive surgical procedure) seen in breast cancer patients with preoperative ionizing radiation.

16.2 Primary and Secondary Endpoints

16.21 Primary Endpoint: The pathologic complete response (pCR) rate observed at time of definitive surgery in breast cancer patients receiving preoperative ionizing radiation. A residual tumor cancer burden 0-1 would be considered a pCR.³¹ All patients meeting eligibility criteria who have signed a consent form and who have begun treatment will be evaluable for the endpoint.

16.22 Secondary Endpoints:

16.221 Acute and late adverse events including grade ≥ 2 pneumonitis.

16.223 Locoregional control, invasive disease-free, distant recurrence, disease-free survival, cause-specific survival, overall survival.

The following definitions are used for the secondary endpoints of interest:

- *Pathologic complete response*: We defined a pathological complete response (pCR) as a residual tumor burden of 0-1 in the surgical specimen.³¹
- *Acute adverse events* (up to 180 days post-RT): any adverse event, regardless of attribution, that occurs in the first month post-RT.
- *Late adverse events* (up to 5 years post XRT): any adverse event that occurred after the first month post-RT and up to 5 years post-RT.
- *Ipsilateral breast tumor recurrence (IBTR)*: this is defined as local recurrence from trial registration as a first event at 5 years. IBTR is defined as both invasive and non-invasive breast cancer involving the same breast parenchyma as the original tumor.
- *Regional recurrence*: invasive breast cancer in the axilla, regional lymph nodes, chest wall, and skin of the ipsilateral breast at 5 years.
- *Distant recurrence*: metastatic cancer that has either been biopsy confirmed or clinically diagnosed as recurrent invasive breast cancer at 5 years.
- *Invasive disease-free survival*: this is defined as the time from study registration until the occurrence of one of the events in a composite endpoint. This endpoint includes invasive IBTR, regional invasive breast cancer recurrence, distant breast cancer recurrence, death due to any cause,
- *Disease-free survival*: this is defined as the time from study registration until the occurrence of one of the events in a composite endpoint. This endpoint includes any IBTR, regional invasive breast cancer recurrence, distant breast cancer recurrence, death due to any cause,
- *Cause specific survival*: is defined as the time from registration to death due to breast cancer. If the cause of death is unknown or difficult to establish, patients with a distant failure at the time of death would be censored as dying from breast cancer
- *Overall survival*: is defined as the time from registration to death due to any cause.

16.3 Exploratory endpoints:

16.31 Patient self-reported cosmesis, i.e. fatigue, breast pain, and other patient reported outcomes.

16.32 Clinical features, treatment technique, dose-volume parameters, histologic and genetic variants associated with adverse events, and fair and poor cosmetic outcomes or unplanned surgical intervention.

16.33 Tumor mutation signatures before and after radiation; correlate tumor mutation signatures before and after radiation with pathologic information at the time of surgery.

16.34 Pathologic changes seen in breast cancer patients with preoperative radiation.

The following definitions are used for the exploratory endpoints of interest:

- *Patient Reported Outcomes/Quality of life:* Elements of the Patient-Reported Outcomes Version of the Common Terminology Criteria for Adverse Events (PRO-CTCAE) will be used for patient self-reporting of toxicities. The Breast Cancer Treatment Outcomes Scale (BCTOS) will be used to measure patient reported functional status (pain, mobility). Other measures of fatigue, pain, and arm function are listed in the appendix.

- *Provider reported cosmetic outcomes*: the physician or mid-level reported outcome will be assessed using the Harvard Cosmesis Scale baseline, EOT, 3 months, 12 months, and yearly after.
- *Patient self-reported cosmetic outcomes*: the patient self-reported outcome will be assessed using a modified Harvard Cosmesis Scale and the BCTOS at baseline, 2 years, and 5 years.
- *Panel assessed cosmetic outcome*: in addition to patient self-reported and physician reported outcomes, cosmesis will be assessed by a panel of breast cancer medical providers using digital photographs from baseline and at 2 years.

16.4 Statistical Design:

Pathologic complete response (pCR) will be assessed at the time of definitive surgery. The largest success proportion where the proposed treatment regimen would be considered ineffective in this population is 5%, and the smallest success proportion that would warrant subsequent studies with the proposed regimen would be 20%. The following Simon's Optimum design uses 22 evaluable patients to test the null hypothesis that the proportion of successes is at most 5%

16.41 Decision Rules:

16.411 If 2 or fewer successes are observed in the first 22 evaluable patients that have a definitive surgical procedure, we will consider this regimen to be ineffective in this patient population. If 3 or more successes are observed in the first 22 evaluable patients, we may recommend further testing of this regimen in subsequent studies in this patient population.

16.412 Over Accrual: If more than the target number of patients are accrued, the additional patients will not be used to evaluate the stopping rule or used in any decision making process.

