3.0 Patient Eligibility

3.1 Inclusion Criteria

- 3.1.2 Age ≥ 18 years.
- 3.1.3 Histological confirmation of breast cancer.
- 3.1.4 Clinical Stage T0-T2 N0 M0.
- 3.1.5 ECOG Performance Status (PS) 0 to 2. (Appendix I)
- 3.1.6 Able to and provides IRB approved study specific written informed consent.
- 3.1.7a Study entry must be within 120 days of last biopsy (breast).
- 3.1.7b Able to complete all mandatory tests listed in section 4.0.
- 3.1.7c Willing to return to enrolling institution for follow-up (during the active monitoring phase of the study).
- 3.1.8 Planned breast surgery and indications for whole breast radiotherapy.
- 3.1.9 No neo-adjuvant therapy

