7.11 Surgery

7.11.1 Surgical treatment will be done at the discretion of the treating surgeon.
7.11.2 Surgery will be done at 8 weeks after the completion of radiation.
Acceptable range is 4-16 weeks after.

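### The primary-analysis set is defined inconsistently (begun, completed or operated), and the plan does not say how a patient without a surgical specimen is counted

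*Combined protocol and SAP*

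**What the plan says.** The combined protocol and SAP describes the patients behind the primary endpoint in several places.

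- **16.21 (and, in near-identical terms, 16.51):** "All patients meeting eligibility criteria who have signed a consent form and who have begun treatment will be evaluable for the endpoint".
- **6.1.3, on evaluability:** eligible patients "who have signed a consent form and who have completed treatment will be evaluable for the primary analysis".
- **6.1.3, on accrual:** patients completing "pre-op RT followed by breast conserving surgery will be used to determine the protocol accrual".
- **6.1.4:** "All patient meeting accrual as defined in 6.1.3 will be analyzed per study".
- **16.411, failure sentence:** the regimen is considered ineffective "If 2 or fewer successes are observed in the first 22 evaluable patients that have a definitive surgical procedure". The success sentence (3 or more) refers to the first 22 evaluable patients and does not mention surgery.
- **16.511:** the pCR proportion is successes over all evaluable patients.
- **16.412 and 16.512:** patients beyond the target stay out of the decision; 16.512 puts them in the final estimate and confidence limits.
- **16.42:** 22 evaluable patients plus 3 spares, for ineligibility, cancellation, major treatment violations and other causes.

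On surgery, 3.1.8 requires "Planned breast surgery and indications for whole breast radiotherapy". Section 7.11.1 says "Surgical treatment will be done at the discretion of the treating surgeon", and 7.11.2 gives the timing after RT: "Acceptable range is 4-16 weeks after".

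**The concern.** A patient who starts RT and stops early is in the primary analysis under 16.21 and 16.51, and out of it under 6.1.3. A patient who starts RT and is never operated on is evaluable under 16.21 and 16.51, and so sits in the 16.511 denominator. The same patient is left out of the 22 by the failure sentence of 16.411 but not, on its words, by the success sentence. A patient whose definitive operation is not breast conserving fits 16.411 but not the accrual definition in 6.1.3 and 6.1.4.

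This is an open, single-arm trial with a cut-off of three successes, so one patient's inclusion can settle the outcome. Suppose 22 patients have begun RT, 21 have been operated on, and 2 have a pCR. If the 22 are patients who began RT, the result is final: 2 of 22, ineffective. If the 22 are operated patients, one more is awaited and the rule can still be met. With the set unsettled, that choice could be made after the pCR results are known.

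**Working it through.** **Inputs.** Null rate 5% and target rate 20% (16.4); rule of 3 or more successes in 22 (16.411); nominal significance level 0.10 and the table of probabilities (16.44); 3 spare patients, 25 in all (16.42). The documents give no rate of missed surgery. I assume 1 to 3 of 22, the upper end being the whole 16.42 allowance.

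**Step 1: reproduce 16.44.** With X binomial(22, p), P(X ≥ 3) = 1 − P(0) − P(1) − P(2). At p = 0.20 this is 1 − 0.0074 − 0.0406 − 0.1065 = 0.8455.

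| True rate | 0.05 | 0.10 | 0.15 | 0.20 | 0.25 |
|---|---|---|---|---|---|
| Recomputed | 0.0948 | 0.3800 | 0.6618 | 0.8455 | 0.9394 |
| 16.44 | 0.09 | 0.38 | 0.66 | 0.85 | 0.94 |

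The table is correct for 22 patients who each have success probability p.

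**Step 2: which 22 patients the table describes.** Two readings make it exact:

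- 22 operated patients, with 5% and 20% as rates among operated patients; or
- 22 patients who began RT, with 5% and 20% as rates among those who began RT and no specimen counted as non-pCR.

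Section 16.4 refers only to the population, so the plan does not choose between them.

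**Step 3: the mixed reading.** Take 5% and 20% as rates among operated patients, but use the begun-RT set of 16.21 and 16.51. If m of the 22 are not operated on and count as non-pCR, only 22 − m can succeed, and the probability of passing is P(X ≥ 3 | 22 − m, p).

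| Unoperated, m | Alpha (p = 0.05) | Power (p = 0.20) |
|---|---|---|
| 0 | 0.0948 | 0.8455 |
| 1 | 0.0849 | 0.8213 |
| 2 | 0.0755 | 0.7939 |
| 3 | 0.0665 | 0.7631 |

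At the extreme, m = 3, power falls by 0.8455 − 0.7631 = 0.0824, about 8 points. Alpha also falls, so the mixed reading makes the test more conservative and does not inflate the false-positive rate.

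**Step 4: whether the over-accrual clauses explain the difference.** Sections 16.412 and 16.512 let decision and estimate differ only for patients beyond the target. A patient within the target who began RT and was not operated on is not over-accrual, so the clauses do not cover that case.

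**The case against.** Several points on the other side stand.

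- **Fewer sets may be intended.** Surgery is section 7.11, under the protocol-treatment heading 7.0, so completing treatment in 6.1.3 may include surgery. That would bring 6.1.3 close to the failure sentence of 16.411. The begun-treatment sentences and the 16.511 denominator would still conflict with it.
- **The loss is hypothetical.** Planned surgery is an entry criterion and RT is five fractions, so few patients may miss surgery. This limits the size of the problem but does not remove the contradiction.

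A reader might also infer more than the documents support.

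- **That the 3-of-22 rule is confined to operated patients.** Only its failure sentence says so. The condition may be meant to carry over, but that has to be inferred.
- **That 16.5 defines an operated analysis set.** It ties the earliest expected release of results to 22 operated patients. It sets a date, not a denominator.
- **That 16.44 is wrong, or that true power is 0.76 to 0.82.** Those values need both assumptions of Step 3. If 5% and 20% are rates among patients who began RT, with no specimen counted as non-pCR, 16.44 holds whatever the missed-surgery rate.
- **That 25 starters, 22 operations and 3 pCRs show the gap, with 3/22 = 13.6% deciding and 3/25 = 12.0% reported.** With a target of 22 and the begun-RT set, 3 of those 25 are beyond the target, and 16.512 already puts them in the estimate only. The example therefore mixes in a difference that the plan intends.

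**Conclusion.** The point holds and should be fixed. Sections 6.1.3, 16.21/16.51, 16.411 and 16.511 cannot all be followed as written, and the handling of a patient who begins RT but has no specimen is not stated. The arithmetic of the design is sound; what is unsettled is which patients it applies to.

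The size is modest: about 2 to 8 points of power for 1 to 3 unoperated patients of 22. This rests on an assumed number of missed surgeries, on 5% and 20% being rates among operated patients, and on use of the begun-RT set. It is nil if every patient who starts RT completes it and has breast conserving surgery. Confidence in the textual conflict is high.

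**What to change.** Before the primary analysis, state one evaluable set and use it in 6.1.3, 6.1.4, 16.21, both sentences of 16.411, 16.51 and 16.511. Say how a patient without a surgical specimen is counted, whether any definitive surgery qualifies for the analysis, and which set 5% and 20% describe. Because the interval to surgery varies, also state the order in which the first 22 are taken. Keep 16.512 as the only difference between the decision and estimation sets.

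Either definition is workable.

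- **(i) Begun RT, no specimen counted as non-pCR.** Section 16.44 stands if 5% and 20% are redefined for this set. Otherwise restate it for an assumed surgery rate. With loss rate d, the same rule on n starters gives P(X ≥ 3 | n, p(1 − d)): alpha 0.094 and power 0.840 for n = 23 at 5% loss, and 0.091 and 0.833 for n = 24 at 10% loss. These use 1 or 2 of the 3 spares. The replacement reasons in 16.42 need aligning, since a patient with a treatment violation who began RT would remain evaluable.
- **(ii) Operated only.** Section 16.44 is unchanged provided 22 patients are operated on, and the 3 spares must also cover ineligibility, cancellation and violations. The downside is that leaving out patients who start RT but are not operated on can raise the reported pCR rate, so the begun-RT proportion should be reported alongside.

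The cost is wording under either option, plus one extra reported proportion under (ii).
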